The combination of chemotherapy agents achieves remission in 80-90% of children with ALL, especially with intensive protocols of 6-8 drugs in 4-8 weeks in the remission induction and consolidation phases, achieving in our days rates of up to 85% event-free survival and 90% overall survival, in developed countries.³

Current regimens include induction therapy consisting of 4-6 weeks and include steroid, vincristine, asparaginase, anthracyclines and intrathecal therapy. Consolidation includes 6 months of a combination of

intense chemotherapy that is designed to consolidate remission and prevent the development of leukemia in the central nervous system. This phase includes high-dose methotrexate. And finally, patients receive maintenance treatment with low-intensity chemotherapy for 18 to 30 months.³ Another important part of the treatment is therapy directed to the central nervous system.^{16,17}

Treatment failure occurs in 15-20% of children with ALL in developed countries, leading to lower cure rates after relapse. When relapse occurs during treatment, the probability of achieving a second remission is 50-70% and only 20-30% of patients are cured.^{18,19}

ALL in adolescents

The treatment of adolescents with ALL has always been challenging, as the mere fact of being older than 10 years carries an adverse prognosis. These patients diagnosed with ALL have shown very little prognostic benefit compared to younger patients with ALL younger than 10 years. It has even been reported that adolescents and young adults have 7.7 to 10.5 times higher risk of relapse compared to children between 1 and 10 years of age.²⁰ The factors that cause this age group to have worse survival rates are unknown. Some proposals are heterogeneity in the biology of leukemia, host factors, both physiological and psychosocial, and the therapeutic approach proposed by the health care team.²¹⁻²³

Multidrug resistance (MDR)

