What is the effect of metformin use on ABCB1/MDR1 and AMPK gene expression in the remission induction phase in adolescent patients with newly diagnosed ALL?

PROBLEM STATEMENT

ALL is the most common oncologic disease in the pediatric population, representing 35% of childhood cancer cases in world statistics, and up to almost 50% according to Mexico's national statistics. In countries with limited resources, long-term survival is reported to be greater than 90%. In countries such as Mexico, the 5 year overall survival of this disease has been described to be around 50%, and in those patients with poor prognostic factors even lower, including adolescents.

The expression of the ABCB1/MDR1 and AMPK gene in adolescents, as well as in patients with ALL and its variation during treatment, is currently unknown.

In recent years, the use of metformin has proven to be useful in the treatment of different hematological malignancies and solid tumors, such as breast cancer and leukemia, through different metabolic pathways. Although the usefulness of this drug has been demonstrated in adults, in pediatrics it is still an unproven field. Clinical trials in children and adolescents are beginning to be conducted in refractory or relapsed solid tumors; however, there are none in acute lymphoblastic leukemia.

To date, the benefit of metformin use in ALL in pediatrics, especially in the high-risk group of adolescents, and the interaction it may have with ABCB1/MDR1 and AMPK gene expression, has not been reported. Therefore, it is necessary to evaluate the expression of these genes and the usefulness of metformin in adolescents with acute lymphoblastic leukemia.

JUSTIFICATION

The description of ABCB1/MDR1 and AMPK gene expression in adolescents with ALL may help to understand their involvement in the biological behavior of ALL in this population.

The search for new alternatives in cancer treatment to improve patient survival is one of the main objectives of current research. The repositioning of old drugs in cancer treatment is one of the lines being analyzed, as is the case of metformin.

In basic and clinical studies, the antineoplastic activity of metformin has been demonstrated. It has been studied in breast cancer, prostate cancer and hematological neoplasms, all in adults. Therefore, transferring these studies to other populations, such as adolescents, may contribute to improve the survival rate in this group with poor prognosis in ALL.

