The generation of knowledge regarding the usefulness of metformin in this specific group of patients can lay the groundwork for research on the effect of this drug in solid tumors and other pediatric neoplasms.

HYPOTHESIS

If metformin is added to standard chemotherapy during the remission induction phase in Mexican adolescents with newly diagnosed ALL, then it will decrease the level of ABCB1/MDR1 gene mRNA expression and increase AMPK expression levels, at the end of this treatment period.

OBJECTIVES

General:

- To evaluate the efficacy of metformin in modifying ABCB1 and AMPK gene expression in adolescents diagnosed with ALL during the remission induction phase.

Specific

- To describe the expression levels of ABCB1/MDR1 and AMPK genes in adolescents with ALL at diagnosis and in healthy controls.
- To compare the expression levels of ABCB1/MDR1 and AMPK genes at diagnosis and at the end of induction in adolescents with ALL treated with conventional chemotherapy and those additionally treated with metformin.
- To compare overall and disease-free survival in adolescents with ALL treated in relation to ABCB1/MDR1, and AMPK gene expression.
- To compare overall and disease-free survival in adolescents with ALL treated with conventional chemotherapy with those treated with conventional chemotherapy plus metformin.

METHODOLOGY

Type and design of study

Type of study: randomized clinical trial

Study design: analytical, experimental, longitudinal and prospective study.

Population

The population to be studied are patients with newly diagnosed ALL between 10 and 21 years.

Eligible population: patients with newly diagnosed ALL between 10 and 21 years old, diagnosed at the Hospital General de México "[name]" from February 2021 to December 2023.

Inclusion, exclusion and elimination criteria

- Inclusion criteria:
 1. Patients aged between 10 and 21 years with a new diagnosis of ALL at the Hospital General de México, [name].
 2. Patients and legally authorized person who sign the informed consent.

- Exclusion criteria:
 1. Patients with antineoplastic treatment prior to admission.
 2. Patients with Down syndrome.

- Elimination criteria:
 1. Patients who abandon treatment for more than a few weeks.4
 2. Patients who withdraw informed consent

Sample size

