To calculate the sample size, we used data from the publication by Ramos Peñafiel⁶³, where a decrease in the expression pattern of ABCB1 gene expression from high to low expression after metformin administration was 50%.

The sample size calculation was based on the formula for estimating a proportion, with a confidence level of 95% and a precision of 5%:

$$n = \frac{Z_{\alpha}^2 * p * q}{d^2}$$

A sample number of 8 patients in each group is obtained, assuming a loss of 20%, 10 patients are calculated for each group.

Definition of the variables to be evaluated and how they are to be measured

Variable	Conceptual Definition	Unit of measurement	Type of variable	Coding
Age	Time elapsed in years since birth.	Years	Quantitative	Not applicable

Gender	Male or female phenotype of the person.	Male/female	Qualitative Dichotomous	0: male 1: female
Leukocyte count at diagnosis	Number of total leukocytes reported on complete blood count at diagnosis.	X10/ml ³	Quantitative	Not applicable
Hemoglobin at diagnosis	Measurement of the amount of oxygen transport protein reported in initial complete blood count.	g/dL	Quantitative	Not applicable
Platelet count at diagnosis	Measurement of the number of platelet fragments produced by the megakaryocytes, reported in the initial complete blood count.	X10/ml ³	Quantitative	Not applicable
Immunophenotype of leukemia lymphoblastic	Cellular variant of acute lymphoblastic leukemia	B/ T	Qualitative dichotomous	0: strain B 1: lineage T
Cytogenetic alterations	Alterations in the genetic structure of leukemic cells.	None/ t(9;22)/ t(12,21)/ t(4,11), other	Qualitative polytomous	0: none 1: t(9;22), 2: t(12,21) , 3: t(4,11), 4: other
MDR-1 and AMPK gene expression.	Amplification of gene expression by RT-PCR	No expression / low expression / high expression expression	Qualitative polytomous	0: not expressed 1: high expression 2 low expression
Pre-phase response with prednisone	Decrease in total peripheral blood blast count less than 1000 after 7 days of steroid (day 0)	Present/absent	Qualitative dichotomous	0: Yes 1: No
Morphological status at day +14	Presence of blasts in bone marrow sample per day +14 referral induction	M1, M2, M3	Qualitative polytomous	0: M1 1: M2 2: M3
Morphological response at the end of induction	Presence of blasts in the bone marrow aspirate at the completion of remission induction phase.	M1, M2, M3	Qualitative polytomous	0: M1 1: M2 2: M3

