The assignment will be made by means of the block randomization technique, in which, from a table of random digits, two-digit numbers are selected, each of which corresponds to a block of 6 patients, to which the intervention is assigned in the corresponding sequence.

All patients will start treatment with steroid window, with prednisone at a dose of 60mgm2Seday (maximum dose 100mg/d), for 7 days (from day -7 to-1). Patients in the study group (treatment with conventional chemotherapy + metformin) are added metformin hydrochloride orally, at a dose of 1000mgm2Seday, divided into two doses, with a maximum dose of 850mg every 8 h starting from day -7 of treatment. On day 0 the response to the pre-phase with prednisone (60mgm2scd) will be assessed by means of blood biometry with differential count and blast count.

Both groups will start remission induction and consolidation treatment according to the Institutional High Risk protocol, which includes administration of vincristine, prednisone, daunorubicin and L-asparaginase. Patients assigned to intervention group will also continue with metformin at the established doses.

A bone marrow exam will be performed at day +14 of remission induction to determine the marrow response to chemotherapy. A bone marrow aspirate will be performed at the end of remission induction to evaluate the response to this phase of treatment with morphological study and minimal residual disease, as well as determination of the expression of the ABCB1/MDR1 and AMPK gene with the methodology described above. At the end of remission induction, metformin will be discontinued in group assigned to it.

Patients will be followed up for 12 months from the start of treatment, and any relapses of the disease or deaths, as well as the time at which they were diagnosed, will be recorded on the data collection sheet.

STATISTICAL ANALYSIS

Data analysis will be carried out using the Statistical Package for Social Sciences (SPSS) version 25.0. Descriptive data will be expressed in percentages and absolute values for qualitative variables, and will be described in medians, ranges, means and standard deviation for quantitative variables.

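### The fixed 12-month follow-up discards survival follow-up that will already have happened for earlier patients; a common closing date would recover it with no extra patients and no later end date

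*Combined protocol and SAP*

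**What the plan says.** The Procedures section fixes the horizon for each patient: "Patients will be followed up for 12 months from the start of treatment". Relapses, deaths and their dates are recorded within that period. The Population section admits patients diagnosed "from February 2021 to December 2023". No common closing date is given anywhere.

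Two of the four specific objectives concern survival. One is "To compare overall and disease-free survival in adolescents with ALL treated with conventional chemotherapy with those treated with conventional chemotherapy plus metformin"; the other relates survival to expression of the two genes. The Statistical Analysis section plans Kaplan-Meier curves and log-rank tests for overall and disease-free survival, by arm and by gene expression. It states no event target, effect size, significance level or power for them.

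On size, the plan says: "A sample number of 8 patients in each group is obtained, assuming a loss of 20%, 10 patients are calculated for each group". The general objective and the hypothesis concern gene expression at the end of induction, not survival.

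**The concern.** Under the plan as written, the trial cannot finish its survival data until the last patient has been followed for 12 months, which is about December 2024 if recruitment uses the whole window. By then a patient who started in early 2021 could have nearly four years of follow-up. The plan counts one year and ignores the rest.

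The outcomes of interest extend well beyond 12 months. The background says that after induction and 6 months of consolidation, "patients receive maintenance treatment with low-intensity chemotherapy for 18 to 30 months". The only local survival figure is a 5-year one. Curves cut at 12 months say nothing about later relapse or death. In a trial of 20 patients each additional event matters, and these events can be had from the same patients without prolonging the trial.

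**Working it through.** **The plan's own figure.** There is no survival calculation to reproduce. The only sizing is for estimating a proportion, "with a confidence level of 95% and a precision of 5"%, using a proportion of 50% from the cited study. Those inputs give n = 1.96² × 0.5 × 0.5 / 0.05² = 384.2, so 385, and not 8; a result of 8 needs a precision of about 0.35. The step from 8 to 10 is right (8 / 0.8 = 10). For this point, what matters is that the 20 patients were not chosen with survival in mind.

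**Inputs from the documents**
- 20 patients, 10 per group (Sample size).
- 12 months of follow-up each (Procedures).
- A recruitment window of 11 + 12 + 12 = 35 months (Population).
- 5-year survival: "the 5 year overall survival of this disease has been described to be around 50"%, and lower in adolescents, by an amount not stated (Problem Statement).

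**Assumptions, not in the documents**
- Constant hazard and uniform entry over all 35 months (both varied below).
- No losses.
- Two-sided 5% level.

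**Potential follow-up.** With the 12-month cut: 20 × 12 = 240 patient-months. With a common close 12 months after the last entry, follow-up runs from 12 to 47 months with a mean of 29.5: 20 × 29.5 = 590 patient-months, before deaths and losses.

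**Expected deaths, base case.** h = ln 2 / 60 = 0.01155 per month.
- 12-month cut: 1 − exp(−12h) = 1 − 0.8706 = 0.129; × 20 = 2.59.
- Common close: 1 − [exp(−12h) − exp(−47h)] / (35h) = 1 − (0.8706 − 0.5810) / 0.4043 = 0.284; × 20 = 5.68.
- Share lost: 1 − 2.59 / 5.68 = 54%.

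**Sensitivity of the share lost** (5-year survival 50% unless stated)

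| Scenario | Deaths, 12-month cut | Deaths, common close | Share lost |
|---|---|---|---|
| Base case | 2.6 | 5.7 | 54% |
| 5-year survival 30% | 4.3 | 8.7 | 51% |
| 5-year survival 60% | 1.9 | 4.4 | 56% |
| Rising hazard, Weibull shape 1.2 | 1.9 | 5.1 | 62% |
| Falling hazard, shape 0.85 | 3.2 | 6.2 | 48% |
| Falling hazard, shape 0.7 | 4.0 | 6.7 | 40% |
| Falling hazard, shape 0.5 | 5.3 | 7.6 | 29% |
| Cured fraction, uncured median 1 to 2 years | 5.2 to 3.6 | 8.1 to 6.7 | 36–47% |
| Constant hazard, accrual in 24 months | 2.6 | 4.8 | 46% |
| Constant hazard, accrual in 12 months | 2.6 | 3.7 | 31% |
| Shape 0.5 and accrual in 12 months | 5.3 | 6.3 | 15% |

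The survival level hardly moves the share; hazard shape and accrual time do. With the plan's 20% loss (16 patients) the base case is 2.1 against 4.5 deaths, the same share.

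**What this does for the test.** Schoenfeld approximation at hazard ratio 0.5, with the base-case deaths: power = Φ(0.693 × √d / 2 − 1.96).
- d = 2.59: Φ(0.558 − 1.96) = 8%.
- d = 5.68: Φ(0.826 − 1.96) = 13%.

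The approximation is rough at such counts. Simulating the log-rank test gives rejection rates of 1.8% and 8.9% at hazard ratio 0.5, and 2% and 19% at 0.2. For 80% power at hazard ratio 0.5 about 4 × (1.96 + 0.842)² / 0.693² = 65.3, so 66 deaths, are needed.

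**The case against.** A fixed horizon with equal follow-up is a defensible choice, survival is not the general objective, and 20 patients cannot support a survival comparison whatever the follow-up. All of that stands. It limits how much the point matters, but it gives no reason to leave available follow-up uncounted.

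Three stronger readings are tempting, and the documents support none of them.

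- A reader might infer that more than half of the deaths are discarded. That needs a constant or rising hazard and accrual over nearly the whole window. The window defines eligibility; the plan does not say that 20 patients will take 35 months to enrol, and it gives no hazard shape.
- A reader might infer that the cut is what usually leaves the log-rank test unable to reach significance. At 10 against 10, three deaths all in one arm give p = 0.067 and four give 0.029 (an exact test needs five). In the base case the chance of four or more deaths by 12 months is 25%, rising to 86% with a common close. But at 5-year survival of 30% it is already 65% with the cut, and at Weibull shape 0.7 it is 59%. These are chances that significance is possible at all; they are not power. They also cover deaths only: disease-free survival adds relapses, for which the documents give no rate, and group sizes by gene expression are unknown.
- A reader might infer that every patient is still on therapy at 12 months. The durations in the background describe current regimens in general; the total length of the institutional protocol is not given.

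**Conclusion.** The point holds as an inexpensive improvement to the survival objectives. The plan stops counting at 12 months although the trial must remain open longer for all but the last patients, and no passage sets a later date.

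In the base case about 2.6 deaths are counted instead of about 5.7. Given what the documents leave open, the share lost is best stated as roughly 15–60%; it is above zero in every scenario examined. Relapses are truncated in the same way, by an amount that cannot be sized.

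The benefit is longer curves and more precise estimates. The number of patients remains the dominant limit on the log-rank test, so a non-significant survival comparison would be uninformative with or without the change. The gene-expression objective is not touched.

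**What to change.** Replace the follow-up sentence in Procedures with:

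> All patients will be followed for relapse and death until a common closing date, 12 months after the last patient starts treatment; patients without the event are censored at that date or at last contact.

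In the Statistical Analysis section, keep the 12-month Kaplan-Meier estimate as a landmark, so that nothing now planned is lost. Report estimates with 95% confidence intervals, and label the overall and disease-free survival comparisons as descriptive.

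The change needs no additional patients and no later end date. It does require chart review of patients treated earlier at the same hospital, some of whom may be lost to contact. Follow-up becomes unequal, which Kaplan-Meier and log-rank methods handle through censoring. The sponsor should also confirm that consent covers follow-up beyond 12 months; the consent pages are not available here, so this could not be checked.

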Minimal residual disease at the end of induction.	Flow cytometry measurement of the presence of 1x10 ⁻³ blasts.	Positive /Negative	Qualitative dichotomous	0: positive 1: negative
Relapse	Presence of blasts in bone marrow after remission has been achieved.	Present/absent	Qualitative dichotomous	0: absent 1: present

Time to relapse	Time from diagnosis of leukemia to relapse	Days	Quantitative	Not applicable
Death	Cessation of life	Present/absent	Qualitative dichotomous	0: absent 1: present
Time to death	Time from leukemia diagnosis to death	Days	Quantitative	Not applicable

Table 1. Variable definitions.

PROCEDURES

Patients with a newly morphological diagnosis of ALL at the Hospital General de México "[name]" will be invited to participate in this trial, and informed consent will be requested from parents and participants.

The data collection is obtained from the patients chart such as age, gender, leukocyte count, hemoglobin, platelet count and immunophenotype.

Peripheral blood samples will be collected in EDTA tube. The sample will be centrifuged obtaining mononuclear cells, and the analysis of ABCB1 and AMPK expression will be performed. This will be done on samples obtained before the start of treatment and at the end of the induction phase. Samples will be collected by peripheral vein puncture, and mononuclear cells will be separated using density gradient. Mononuclear cells are separated and suspended in PBS medium and stored at -70°C . RNA isolation is performed using TRIzol® (Invitrogen/life Technologies), and will be stored at -80°C until use. For cDNA synthesis, 2g of RNA, final volume of 20L will be combined with 200U of MMLV RT enzyme (Invitrogen, Carlsbad, CA, USA).

Expression of mRNA levels will be measured using the TaqMan gene expression assay (Applied Biosystems Foster city, CA, USA). The cut-off point between low and high expression will be determined according to mean values obtained in healthy controls, selected during case recruitment in a 2:1 ratio for each case.

Regarding treatment, patients will be randomized into 2 groups, where in both cases the conventional remission induction treatment will be given, and to intervention group metformin will be added at a dose of 1000mgm2Seday, divided into two doses, with a maximum dose of 850mg every 8 hour, orally.

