The Kolmogorov-Smirnov test will be performed for continuous variables to determine if they have normal distribution; if they have normal distribution, both groups will be analyzed by means of the t-student test; if they do not have normal distribution, the chi-square test, Fisher's exact test and Mann Whitney U test will be used for the bivariate analysis. To compare the expression of ABCB1/MDR1 and AMPK genes at the time of diagnosis and at the end of induction, McNemar's test will be used.

For the calculation of the overall and disease-free survival function, the Kaplan Meier survival test will be used for both groups and the differences between groups will be analyzed by means of the log Rank test, both for overall and disease-free survival. Similarly, the overall and disease-free survival function will be analyzed with the Kaplan Meier test and log rank for ABCB1/MDR1 and AMPK gene expression.

ETHICAL AND BIOSAFETY ASPECTS

According to the General Health Law regarding research on human subjects, this protocol is considered a higher than minimal risk research, since randomized methods of assignment to therapeutic schemes are used.

This protocol takes into account the Mexican General Health Law regarding the provision of health care services and health research, as well as national and international ethical standards.

This study will be carried out with strict observance of recognized scientific principles and respect and confidential handling of the data obtained. The security mechanisms to maintain the ethical aspects of this study are:

1. Review of this protocol by the research and ethics committees of the Hospital General de México "[name]".
2. All information obtained in this study will be made available to the Ethics and Research Committees.
3. The confidentiality of the study information is assured, as well as the identity of the patients. The identification data of the participants will be codified, assigning a consecutive participation number. The identification information and the relation between the identification numbers and the data obtained will be known only to the participating investigators and will be preserved confidentially in electronic media.
4. There will be no charge for the study, nor will there be any consistency for participation in this study. Refusal to participate in the study will not influence the patient's treatment or clinical care.

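### No named between-arm test of ABCB1 or AMPK expression uses the pre-treatment level; adjusting the continuous level for it would be a cheap efficiency improvement, provided the two levels correlate

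*Combined protocol and SAP*

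**What the plan says.** All references are to the combined protocol and SAP.

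- **OBJECTIVES (Specific).** One objective is "To compare the expression levels of ABCB1/MDR1 and AMPK genes at diagnosis and at the end of induction", in patients on conventional chemotherapy and in those also given metformin. The HYPOTHESIS section predicts lower ABCB1/MDR1 mRNA and higher AMPK expression at the end of induction if metformin is added.
- **PROCEDURES.** Expression is measured by TaqMan assay: "This will be done on samples obtained before the start of treatment and at the end of the induction phase". Low and high expression are separated at the mean of healthy controls. Randomisation is in blocks of 6, and no stratification factor is named.
- **Table 1.** Gene expression is a qualitative variable, coded "0: not expressed 1: high expression 2 low expression".
- **Sample size.** "A sample number of 8 patients in each group is obtained, assuming a loss of 20%, 10 patients are calculated for each group".
- **STATISTICAL ANALYSIS.** Continuous variables are first tested for normality; "if they have normal distribution, both groups will be analyzed by means of the t-student test". Otherwise "the chi-square test, Fisher's exact test and Mann Whitney U test will be used for the bivariate analysis". McNemar's test is assigned to the comparison of expression at diagnosis with expression at the end of induction. Survival uses Kaplan-Meier and log-rank. No ANCOVA, regression, stratified test or change score is named.

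**The concern.** The question is a between-arm one, and each patient supplies a pre-treatment value of the variable being compared. No test named for comparing the arms uses that value. McNemar's test does use it, but it asks whether patients change over time, not whether they change more with metformin.

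With about 10 patients per arm there are few ways to gain precision without recruiting more. If pre-treatment and end-of-induction levels are correlated, adjusting for the first removes variance from the second. If the arms differ by chance at baseline, an adjustment that was planned is also easier to defend than one added after the imbalance is seen.

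**Working it through.** **The plan's own figure.** The plan states no power, SD, between-arm effect or baseline-to-end correlation, so there is no planned power to reproduce. Its only calculation is the sample size. With p = 0.5, 95% confidence and precision 0.05, the printed formula gives 1.96² × 0.5 × 0.5 / 0.05² = 384.2, so 385, not 8. Eight would need a precision of about 0.35, since 1.96 × √(0.25/8) = 0.346. The allowance for loss is correct: 8/0.8 = 10. The mismatch is a separate matter; the 8 and 10 per arm are used here because they are what the trial will have.

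**Inputs.** From the documents: n = 8 or 10 per arm and, by implication of the 95% level, two-sided α = 0.05. Assumed: continuous log expression with equal SD in both arms, effect d = 1.0 or 1.2 SD, correlation ρ from 0 to 0.7.

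**What adjustment buys and costs.** With n per arm:

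- Unadjusted t-test: variance of the arm difference (SD = 1) is 2/n, on 2n − 2 df.
- ANCOVA: residual variance is multiplied by 1 − ρ². Estimating the slope multiplies the variance, on average, by 1 + 1/(2n − 4). There are 2n − 3 df.
- Variance break-even: (1 − ρ²)(1 + 1/(2n − 4)) = 1, so ρ² = 1/(2n − 3). For n = 10, ρ = √(1/17) = 0.24; for n = 8, ρ = √(1/13) = 0.28. The lost degree of freedom moves break-even slightly higher.
- Change score: variance is multiplied by 2(1 − ρ), which is below 1 only when ρ exceeds 0.5.

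At ρ = 0.5 the residual variance falls by 25%.

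**Simulated power** (bivariate normal, 100,000 trials per cell; change in points in brackets):

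| n per arm | d | t-test | ANCOVA ρ = 0 | ρ = 0.3 | ρ = 0.5 | ρ = 0.7 |
|---|---|---|---|---|---|---|
| 8 | 1.0 | 46% | 43% (−3.1) | 47% (+0.4) | 54% (+7.9) | 70% (+24.1) |
| 8 | 1.2 | 61% | 57% (−3.4) | 61% (+0.4) | 70% (+8.7) | 85% (+24.1) |
| 10 | 1.0 | 56% | 54% (−2.6) | 57% (+1.5) | 65% (+9.2) | 82% (+25.4) |
| 10 | 1.2 | 72% | 69% (−2.9) | 73% (+1.3) | 81% (+8.8) | 93% (+21.1) |

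Repeat runs differ by up to about half a point. A change-score t-test with 10 per arm and d = 1.0 gives 56% at ρ = 0.5, the same as no adjustment, and 43% at ρ = 0.3.

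**Chance imbalance.** The SD of the baseline mean difference is √(2/10) = 0.447, so P(|difference| ≥ 0.5 SD) = P(|Z| ≥ 1.118) = 26%. With 8 per arm it is P(|Z| ≥ 1) = 32%. At ρ = 0.5, a 0.5 SD imbalance shifts the unadjusted estimate by 0.5 × 0.5 = 0.25 SD. Over all randomisations the type I error is about 5% for both methods.

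**The case against.** **The t-test sentence may not govern expression.** It applies to continuous variables, Table 1 makes expression categorical, and McNemar's test is assigned to it separately. This stands. The assay does yield a level, and the hypothesis is worded in levels, so a continuous analysis is available. But the text is ambiguous, and the power figures do not carry over to a Fisher or chi-square comparison. Categorising is also the larger loss: with 10 per arm, d = 1.0 and a cut midway between the arm means, Fisher's test has about 22% power, against 56% for the t-test and 66% for ANCOVA at ρ = 0.5.

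**The baseline is not discarded.** A reader might infer that the plan throws it away. It does not, because McNemar's test uses it within patients. The plan also leaves open whether the t or Mann-Whitney test is run on end values or on changes. What is missing is a named between-arm test that uses the baseline.

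**The gain is not established.** A reader might infer a fixed loss of 8 to 9 points of power. That needs a correlation near 0.5 and an effect of 1.0 to 1.2 SD, and the documents give neither. The correlation could be low: the first sample contains leukaemic cells and the later one may not. In addition, PROCEDURES describes peripheral blood but also lists the end-of-induction measurement with the marrow aspirate. Below a correlation of about 0.25 to 0.3, adjustment does not help.

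**The unadjusted test is valid.** This stands. Chance imbalance is already in its standard error, so the 26% figure describes imprecision and is not evidence of bias or an inflated error rate.

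**Conclusion.** The point holds as an efficiency improvement; the plan is not in error here. Expression is measured at both times, the arm comparison is the main question, and no named between-arm test uses the pre-treatment level.

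For the continuous log level, assuming a 1.0 to 1.2 SD effect and 8 to 10 patients per arm, adjustment changes power by about +8 to +10 points at ρ = 0.5, +21 to +26 at ρ = 0.7 and 0 to +2 at ρ = 0.3, with a loss of about 2.5 to 4 points at ρ = 0. The effect sizes and correlations are assumptions, and the documents do not settle even the sign of the benefit. The case for adjusting is that the possible loss is small and the possible gain considerably larger, using data already being collected. Adjustment does not repair the sample-size calculation.

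**What to change.** In STATISTICAL ANALYSIS, state that for each gene the arm effect is estimated by ANCOVA on the continuous log (delta-Ct) level: end-of-induction level as outcome, randomised arm as factor, and the same gene's pre-treatment level as the only covariate, reporting the adjusted difference with its 95% CI. Use a rank-based ANCOVA or a permutation test of the arm term if residuals are clearly non-normal or some samples fall in the not-expressed category. Keep the unadjusted and categorical comparisons as secondary. A raw change score is not a good substitute, for the reason shown in the working.

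Cost: no new patients or assays, and SPSS 25 fits the model. The text needs slightly more than one sentence. It should make the continuous level the analysed variable alongside the Table 1 coding, name the reference gene or normalisation (none is stated), and say how undetected expression is handled. The statistical price is one degree of freedom and the estimated slope, about 2.5 to 4 points of power if the two levels prove uncorrelated.
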